## **2.3 Randomization (Subject Assignment)**

This is an open-label study. Subject enrollment and dispensation of IP will be performed via the Interactive Response Technology (IRT) system. Priority for enrollment will be given to the phase 1 dose escalation portion before phase 2 dose expansion.

For phase 2 enrollment, if more than 1 dose level is open for enrollment within a selected disease type, the newly enrolled subjects with that disease type will be randomly allocated to 1 of the open dose levels. Randomization will be weighted toward newly opened dose levels, with the allocation ratio based on the number of open slots still available at each dose level.

For example, if dose level 'x' enrolled 3 subjects and dose level 'y' is newly opened for expansion, the next subject would be randomly allocated to dose level 'x' or 'y' with the ratio of 9:12.

When escalation and expansion cohorts are both open for enrollment, enrollment into escalation cohorts takes priority such that subjects who are eligible for both will be preferentially enrolled in the escalation cohorts.

### **3 SAMPLE SIZE**

#### Phase 1 (Dose Escalation)

The sample size for the dose escalation phase is not based on a statistical power calculation. The number of subjects enrolled will be dependent on the DLT incidence. The estimated number of subjects, a minimum of 6 evaluable and up to 18, should provide adequate information for the dose escalation and safety objectives of the study.

#### Phase 2 (Dose Expansion)

The sample size in phase 2 is up to 104 subjects per dose level. Each dose level may enroll up to 52 R/R AML subjects and up to 52 R/R higher risk MDS subjects. The response rate is monitored using the BOP2 design. For AML, with assumption of the efficacious CRc rate is 30% and the inefficacious CRc rate is 15%, the statistical power would be approximately 0.83 while controlling the type I error rate at 0.10. For MDS, with assumption of the efficacious CR + BM CR + PR rate is 25% and the inefficacious CR + BM CR + PR rate is 12%, the statistical power would be approximately 0.83, while controlling the type I error rate at 0.10.

#### China Cohort

The sample size for the China cohort is not based on a statistical power calculation. The planned number of approximately 6 subjects would provide adequate information for the objectives of the cohort.

### **4 ANALYSIS SETS**

In accordance with the International Conference on Harmonization (ICH) recommendations in guidelines E3 and E9, the following analysis sets will be used for the analyses. Full Analysis Set (FAS) and Response Analysis Set (RAS) will be used for efficacy analysis. Safety Analysis Set (SAF) will be used for the analyses of safety variables. Pharmacokinetic Analysis Set (PKAS) will be used for pharmacokinetic analyses. The biomarker pharmacodynamics analysis set (PDAS) will be used for all analyses of pharmacodynamics data. Analysis sets are defined in the protocol section 9.2. All classification criteria for determining membership in FAS, RAS, SAF are programmable. The classification identify variables are defined in the datasets specification. The data from all patients who were enrolled in the study will be included in the data listings. All enrolled subjects are those who signed the informed consent form and were assigned a subject number.

For each dose level group, the number and percentage of subjects will be characterized for all treated subjects and by each analysis set.

#### **4.1 Full Analysis Set**

The full analysis set (FAS) will consist of all subjects who are enrolled and receive at least 1 dose of study treatment. This will be the primary analysis set for efficacy analyses.

## **4.2 Response Analysis Set**

The response analysis set (RAS) will consist of all subjects who are enrolled and receive at least 1 dose of study treatment and have at least 1 post baseline primary efficacy measurement.

## **4.3 Safety Analysis Set**

The safety analysis set (SAF) consists of all subjects who receive at least 1 dose of IP. The SAF will be used for all summaries of the safety data. The SAF will also be used for summaries of demographic and baseline characteristics and all safety and tolerability related variables.

## **4.4 Pharmacokinetic Analysis Set**

The Pharmacokinetics Analysis Set (PKAS) consists of the administered population for which pharmacokinetics data are available at least for 1 time point. Additional subjects may be excluded from the PKAS at the discretion of the pharmacokineticist.

The PKAS is used for all tables and graphical summaries of the PK data.

## **4.5 Pharmacodynamic Analysis Set (*Not Applicable for China*)**

The pharmacodynamic analysis set (PDAS) will include the subjects from the administered population for whom sufficient pharmacodynamic measurements were collected.

The PDAS will be used for all analyses of pharmacodynamic data.

## **4.6 DLT Evaluation Analysis Set**

The DLT Evaluation Analysis Set (DEAS) is defined as all subjects in SAF by excluding the subjects who meet any of the following criteria:

- Subject is discovered to have enrolled without fully satisfying eligibility criteria.
- Subject received less than the planned dose in cycle 1 for reasons other than DLT.
- Subject has no DLT and withdraws from the study before the end of DLT evaluation period.

The DEAS will be used for the analysis of DLT data.

## **5 ENDPOINTS**

### **5.1 Efficacy Endpoints**

#### **5.1.1 Primary Efficacy Endpoint: Remission**

For Phase 2, the primary efficacy endpoint will be CRc rate for subjects with R/R AML and (CR+ BM CR +PR) rate for subjects with R/R higher risk MDS.

- AML
  - For subjects to be classified as being in CRc at a post-baseline visit, they must either achieve CR, CRp or CRI at the visit.

- Complete Remission (CR): For subjects to be classified as being in CR at a post-baseline visit, they must have bone marrow regenerating normal hematopoietic cells and achieve a morphologic leukemia free state and must have an absolute neutrophil count (ANC)  $\geq 1 \times 10^9 /L$  and platelet count  $\geq 100 \times 10^9 /L$ , and normal marrow differential with  $< 5\%$  blasts, and they will be red blood cell (RBC) and platelet transfusion independent (defined as 1 weeks without RBC transfusion and 1 week without platelet transfusion). There must be no presence of Auer rods. There should be no evidence of extramedullary leukemia. The blast counts in peripheral blood must be  $\leq 2\%$ .
- Complete Remission with Incomplete Platelet Recovery (CRp): For subjects to be classified as being in CRp at a post-baseline visit, they must achieve CR except for incomplete platelet recovery ( $< 100 \times 10^9 /L$ ).
- Complete Remission with Incomplete Hematological Recovery (CRI): For subjects to be classified as being in CRI at a post-baseline visit, they must fulfill all the criteria for CR except for incomplete hematological recovery with residual neutropenia (ANC  $< 1 \times 10^9 /L$ ) with or without complete platelet recovery. RBC and platelet transfusion independence is not required.
- Composite Complete Remission (CRC): For subjects to be classified as being in CRC at a post-baseline visit, they must achieve CR, CRp or CRI at the visit.
- Complete Remission with Partial Hematologic Recovery (CRh): For subjects to be classified as CRh at a post-baseline visit, if they have marrow blasts  $< 5\%$ , partial hematologic recovery ANC  $\geq 0.5 \times 10^9 /L$  and platelets  $\geq 50 \times 10^9 /L$ , no evidence of extramedullary leukemia and cannot be classified as CR. The blast counts in peripheral blood must be  $\leq 2\%$ .
- Partial Remission (PR): For subjects to be classified as being in PR at a post-baseline visit, they must have bone marrow regenerating normal hematopoietic cells with evidence of peripheral recovery with no (or only a few regenerating) circulating blasts and with a decrease of at least 50% in the percentage of blasts in the bone marrow aspirate with the total marrow blasts between 5% and 25%. A value of less than or equal to 5% blasts is also considered a PR if Auer rods are present. There should be no evidence of extramedullary leukemia.
- Not Evaluable (NE)/No Response (NR): In the situation where no bone marrow assessments are performed or myeloblast value is missing, blast value from peripheral blood is missing or  $\leq 2\%$ , and extramedullary leukemia is missing or not present, the response will be

classified as NE. In any case response cannot be categorized as CR, CRp, CRi, PR or NE, it will be categorized as NR.

A complete response classification schema is presented in [Table 1](#), below.

**Table 1 Response Classification Schema for AML**

Myeloblast in Bone Marrow Aspirate/Biopsy	Blast in Peripheral Blood	Extramedullary Leukemia	Auer Rod	RBC Transfusion	Platelet Transfusion	ANC	Platelet	Response
<5%	Missing or <=2%	Absent/Missing	Absent/Missing	No	No	$\geq 1 \times 10^9/L$	$\geq 100 \times 10^9/L$	CR
<5%	Missing or <=2%	Absent/Missing	Absent/Missing	No	No	$\geq 1 \times 10^9/L$	< 100 $\times 10^9/L$	CR p
<5%	Missing or <=2%	Absent/Missing	-	-	-	$\geq 0.5 \times 10^9/L$	$\geq 50 \times 10^9/L$	CR h
<5%	Missing or <=2%	Absent/Missing	Absent/Missing	-	-	-	-	CR i
>=5% - <=25% and >=50% decrease from baseline	Missing or <=2%	Absent/Missing	-	-	-	-	-	PR
<5%	Missing or <=2%	Absent/Missing	Present	-	-	-	-	PR
Missing	Missing or <=2%	Absent/Missing	-	-	-	-	-	NE
Any case that cannot be categorized as CR, CR p , CR h , CR i , PR, or NE								NR

- Relapse
  - Relapse after CR, CRh, CRp or CRI is defined as a reappearance of leukemic blasts in the peripheral blood (> 2%) or  $\geq 5\%$  blasts in the bone marrow aspirate not attributable to any other cause or reappearance or new appearance of extramedullary leukemia.
  - Relapse after PR is similarly defined with reappearance of >2% of peripheral blasts and an increase in the percentage of blasts in the bone marrow aspirate to > 25% not attributable to any other cause or reappearance or new appearance of extramedullary leukemia.
- Best Response
  - Best response is defined as the best measured response to treatment for all visits (in the order of CR, CRp, CRI, PR, NR and NE) post-baseline. Subjects who achieve the best response of CR, CRp, CRI or PR will be classified as responders. Subjects who do not achieve at least a best response of PR will be considered non-responders.
- MDS
  - Complete Remission (CR): For subjects to be classified as being in CR at a post-baseline visit, they must have all of the following maintained for a minimum of 4 weeks:
    - Bone marrow evaluation:  $\leq 5\%$  myeloblasts with normal maturation of all cell lines
    - Peripheral blood evaluation:
      - Hemoglobin  $\geq 11$  g/dL
      - Platelets  $\geq 100 \times 10^9$  /L
      - Neutrophils  $\geq 1.0 \times 10^9$ /L
      - 0% blasts in blood
  - Partial Remission (PR): For subjects to be classified as being in PR at a post-baseline visit, they must have all CR criteria if abnormal before treatment except the following for a minimum of 4 weeks:
    - Bone marrow blasts decreased by  $\geq 50\%$  over pretreatment but still  $> 5\%$
    - Cellularity and morphology not relevant
  - Marrow CR: For subjects to be classified as being in marrow CR at a post-baseline visit, they must have all of the following for a minimum of 4 weeks:
    - Bone marrow:  $\leq 5\%$  myeloblasts and decrease by  $\geq 50\%$  over pretreatment
      - Peripheral blood: if HI responses, they will be noted in addition to marrow CR
  - Hematologic Improvement (HI): For subjects to be classified as having hematologic improvement (HI) at a post-baseline visit, they must have 1 measurement of the following, maintained for at least 8 weeks without ongoing cytotoxic therapy:
    - HI – erythroid:

- Hemoglobin increase of  $\geq 1.5$  g/dL or
- For RBC transfusions performed for hemoglobin  $\leq 9.0$  g/dL: reduction in RBC units transfused in 8 weeks by  $\geq 4$  units compared to the number of units transfused in the 8 weeks prior to treatment
- HI – platelets:
  - For pre-treatment platelet count of  $>20 \times 10^9$  /L platelet, absolute increase of  $\geq 30 \times 10^9$  /L
  - For pre-treatment platelet count of  $< 20 \times 10^9$  /L, platelet absolute increase of  $> 20 \times 10^9$  /L and  $\geq 100\%$  increase from pre-treatment level
- HI – neutrophils:
  - Neutrophil count increase of  $\geq 100\%$  from pre-treatment level and an absolute increase of  $> 0.5 \times 10^9$  /L
- Relapse after CR or PR: For subjects to be classified as relapsing after CR or PR requires at least one of:
  - Return to pre-treatment bone marrow blast percentage
  - Decrement of  $\geq 50\%$  from maximum response levels in granulocytes or platelets
  - Transfusion dependence or hemoglobin level  $\geq 1.5$  g/dL lower than prior to therapy
- Stable Disease (SD): For subjects to be classified as having Stable Disease (SD), they must fail to achieve at least PR but show no evidence of progression for  $>8$  weeks
- Progressive Disease (PD): For subjects to be classified as having Progressive Disease (PD), they must show blast level increases depending on prior levels as follows:
  - For patients with:
    - $<5\%$  blasts:  $\geq 50\%$  increase in blasts to  $> 5\%$  blasts
    - $5\%-10\%$  blasts:  $\geq 50\%$  increase to  $> 10\%$  blasts
    - $10\%-20\%$  blasts:  $\geq 50\%$  increase to  $> 20\%$  blasts
    - $20\%-30\%$  blasts:  $\geq 50\%$  increase to  $> 30\%$  blasts
  - Or any of the following:
    - At least 50% decrement from maximum remission/response in granulocytes or platelets
    - Reduction in Hgb by  $\geq 2$  g/dL from maximum remission/response
    - Transfusion dependence: RBC or platelet transfusion after a previous CR, BM CR, PR, or HI response
    - A relapse from CR, BM CR, PR, or HI is also considered PD

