7 STUDY PROCEDURES AND ASSESSMENTS

7.1 Efficacy Assessments

7.1.1 Response Criteria Definitions

7.1.1.1 Acute Myeloid Leukemia Response Criteria

Response to treatment will be defined per modified criteria [Cheson et al, 2003] as outlined below.

- Complete Remission (CR)

For subjects to be classified as being in CR at a post-baseline visit, they must have bone marrow regenerating normal hematopoietic cells and achieve a morphologic leukemia-free state and must have an absolute neutrophil count (ANC) $\geq 1 \times 10^9/L$ and platelet count $\geq 100 \times 10^9/L$, and normal marrow differential with $< 5\%$ blasts, and they will be red blood cell (RBC) and platelet transfusion independent (defined as 1 week without RBC transfusion and 1 week without platelet transfusion). There must be no presence of Auer rods. There should be no evidence of extramedullary leukemia. The blast counts in peripheral blood must be $\leq 2\%$.

- Complete Remission with Incomplete Platelet Recovery (CRp)

For subjects to be classified as being in CRp at a post-baseline visit, they must achieve CR except for incomplete platelet recovery ($< 100 \times 10^9/L$).

- Complete Remission with Incomplete Hematological Recovery (CRI)

For subjects to be classified as being in CRI at a post-baseline visit, they must fulfill all the criteria for CR except for incomplete hematological recovery with residual neutropenia (ANC $< 1 \times 10^9/L$) with or without complete platelet recovery. RBC and platelet transfusion independence is not required.

- Composite Complete Remission (CRC)

For subjects to be classified as being in CRC at a post-baseline visit, they must either achieve CR, CRp or CRI at the visit.

- Complete Remission with Partial Hematologic Recovery (CRh)

For subjects to be classified as CRh at a post-baseline visit, if they have marrow blasts $< 5\%$, partial hematologic recovery ANC $\geq 0.5 \times 10^9/L$ and platelets $\geq 50 \times 10^9/L$, no evidence of extramedullary leukemia and cannot be classified as CR. The blast counts in peripheral blood must be $\leq 2\%$.

- Partial Remission (PR)

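### SAP Table 1 and the text definitions give different rules for CRi, so the AML primary endpoint CRc can be counted in more than one way from the same data

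*SAP*

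**What the plan says.** SAP 5.1.1 says that for CRi subjects "they must fulfill all the criteria for CR except for incomplete hematological recovery with residual neutropenia", and gives the limit as ANC below 1 x 10^9/L, with or without platelet recovery. Protocol 7.1.1.1 has the same ANC limit and adds "RBC and platelet transfusion independence is not required". So platelet recovery and transfusion independence are waived, but the neutropenia condition is not. The CR criteria that CRp and CRi inherit say of peripheral blasts: "The blast counts in peripheral blood must be" at most 2%.

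SAP 5.1.1 then introduces Table 1: "A complete response classification schema is presented in" that table. After the marrow column, its CRi row reads "Missing or <=2% Absent/Missing Absent/Missing - - - - CR", where the final label is CRi with the subscript lost. The ANC cell is a dash. The CR, CRp and CRi rows all accept missing peripheral blasts.

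CRh is also handled in two ways. The Table 1 NR row opens "Any case that cannot be categorized as CR, CR" and goes on to list CRh among the levels. The text NR rule reads "In any case response cannot be categorized as CR, CRp, CRi, PR or NE", without CRh. Best response is ranked "in the order of CR, CRp, CRI, PR, NR and NE", again without CRh.

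SAP 6.4 makes derived response primary and points the derivation to Section 7.1.1. SAP 6.4.1 counts CR, CRp and CRi as CRc.

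**The concern.** CRi counts toward CRc, and the derived CRc rate is the primary AML result. One programmer may work from the table and another from the text. For a subject with cleared marrow and ANC of at least 1 x 10^9/L who was transfused in the preceding week, they can reach different answers. They can also differ when ANC or peripheral blasts are missing. If CRh displaces CRi, subjects who are CRi by the text drop out of CRc.

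The design rates of 15% and 30% are stated for CRc as the text defines it. A count made under another rule is not on the same scale as those rates or as the threshold of 12 responses in 52.

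**Working it through.** **Design figures.** Inputs from protocol 9.1 and 9.4.1.3: looks at 12, 32 and 52 subjects; stop at 1 or fewer responses of 12 and at 5 or fewer of 32; success at 12 or more of 52; rates 0.15 and 0.30. With b(x; n, p) the binomial probability,

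P(success) = sum over x1 >= 2 and x1 + x2 >= 6 of b(x1; 12, p) x b(x2; 20, p) x P(X3 >= 12 - x1 - x2), where X3 ~ Bin(20, p).

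This gives power 0.829 at p = 0.30, which reproduces the stated 0.83, and 0.067 at p = 0.15, within the stated 0.10. SAP 6.7 instead stops at 6 or fewer of 32 (x1 + x2 >= 7), which gives 0.801 and 0.059. That mismatch is a separate matter; both boundaries are carried below.

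**Profiles with complete data.** Hold marrow blasts below 5%, peripheral blasts at most 2%, no extramedullary leukemia and no Auer rods. Cross 3 ANC bands, 3 platelet bands (below 50, 50 to below 100, at least 100) and RBC or platelet transfusion in the preceding week (yes/no): 3 x 3 x 2 = 18. ANC and platelets are in 10^9/L.

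| ANC | Platelets | Transfused | Profiles | Text | Table 1, rows overlap | Table 1, top down |
|---|---|---|---|---|---|---|
| >=1 | >=100 | no | 1 | CR | CR | CR |
| >=1 | <100 | no | 2 | CRp | CRp | CRp |
| >=1 | >=50 | yes | 2 | not CRc | CRi | CRh |
| >=1 | <50 | yes | 1 | not CRc | CRi | CRi |
| 0.5 to <1 | >=50 | either | 4 | CRi | CRi | CRh |
| 0.5 to <1 | <50 | either | 2 | CRi | CRi | CRi |
| <0.5 | any | either | 6 | CRi | CRi | CRi |

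CRc by the text: 1 + 2 + 4 + 2 + 6 = 15. By Table 1 with overlapping rows: 15 + 3 = 18. By Table 1 from the top down: 15 + 1 - 4 = 12. These are counts of profiles, not of subjects.

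**Missing ANC.** This adds 3 platelet bands x 2 = 6 profiles. The 3 without transfusion are CRc whatever the ANC: CRi if it is below 1, CR or CRp otherwise. The 3 with transfusion are CRi if ANC is below 1 and not CRc otherwise, so the text cannot decide. Table 1 codes all 6 as CRi on either reading. Missing ANC therefore matters to CRc only at visits with a recent transfusion.

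**Missing peripheral blasts.** By the text the condition is not shown to be met. By Table 1 the row is satisfied.

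**Sensitivity of the design, on assumed shifts only.** Suppose derived response feeds the BOP2 looks and the coding adds a fixed amount to a true 15%:

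| Shift | P(>=12/52), protocol boundary | P(>=12/52), SAP boundary |
|---|---|---|
| none | 0.067 | 0.059 |
| +1 point | 0.097 | 0.087 |
| +2 points | 0.136 | about 0.12 |
| +3 points | 0.181 | 0.163 |

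Two points are 0.02 x 52 = 1.04 subjects. The documents support no particular shift.

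**The case against.** The best defence is that SAP 6.4 already chooses. The SAP has no Section 7.1.1 that defines response; the protocol does, in text and without a table. On that reading the blank ANC cell never reaches the primary analysis. This carries weight, and it would be wrong to say that the documents give no guidance. But SAP 6.4 does not name the protocol, and SAP 5.1.1 presents Table 1 as the complete schema without saying that the text overrides it.

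The wide CRi row may also be a deliberate residual category. By the text, a transfused subject with cleared marrow and ANC 0.9 is a responder, while one with ANC 1.1 is NR. Table 1 closes that gap. This is a fair reason to ask what was intended, but neither text says it.

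On missing blasts, the text NE rule itself groups missing with at most 2%, and Table 1 treats unrecorded Auer rods and extramedullary status equally leniently. However, the NE rule applies when marrow data are missing. It does not relax the CR requirement. Peripheral blasts are also part of the local hematology panel (protocol Table 12), so a fallback value will often exist. The SAP 6.4 rule against imputing hematology does not help, because a blank already satisfies the row.

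A reader might also infer that central counts are absent by schedule at the week-12 marrow in Observation Period 1, so that marrow alone yields CRi. Protocol Table 3 does place central disease-assessment blood at weeks 4 and 8. But hematology is drawn at week 12, and protocol 10.1 describes submitted local results as centralized data. The inference holds only if centrally evaluated means measured in a central laboratory.

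**Conclusion.** The contradiction stands. Table 1 and the text disagree on the ANC condition for CRi, on missing peripheral blasts and on the place of CRh, and all three bear on the derivation of the AML primary endpoint. It should be fixed.

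The direction is not determined. Against 15 CRc profiles by the text, Table 1 gives 18 or 12 depending on row order, which the SAP does not state. The omission of CRh from the best-response order, together with its own separate rate, favours the overlapping reading but does not settle it. The size is unknown because no frequencies are given.

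A reader might infer that Table 1 inflates CRc and takes the type I error above 0.10. The documents do not support that. It would need the overlapping reading, a net upward shift of about 2 points with no other qualifying visit in those subjects, and derived response as the source for the BOP2 looks, which no section states. The sensitivity figures show only that roughly one subject in 52 matters to this design.

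**What to change.** 1. In the Table 1 CRi row, enter observed ANC below 1 x 10^9/L. Keep the platelet and transfusion dashes, which agree with the text.
2. State in SAP 6.4 that the text of protocol 7.1.1.1 and SAP 5.1.1 governs, naming the protocol in the cross-reference. If the wider residual CRi is intended, amend both texts and justify the 15% and 30% rates for it.
3. Derive CRh as a separate flag that does not displace CRp or CRi, and remove it from the Table 1 NR row.
4. Do not count missing peripheral blasts as met for CRc, nor missing ANC when there was a transfusion in the preceding week. Where the central value is absent, use same-visit local hematology. If that is missing too, count the visit as not CRc.
5. Before relying on transfusion status after end of treatment, reconcile SAP 6.2.5, which records transfusions through end of treatment, with SAP 5.1.11, which needs them to the end of Observation Period 2. Until then it cannot be assumed that no further data are needed.

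The cost is a few SAP edits and some reprogramming, including matching local hematology to marrow visits. If the text governs, step 1 needs no protocol change. The CRc count may move slightly in either direction.

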### 6.4.1 Analysis of Primary Efficacy Endpoints

For Phase 2, the primary efficacy endpoint will be CRc rate for subjects with R/R AML and (CR+ BM CR +PR) rate for subjects with R/R higher risk MDS.

- AML
  - CRc rate is defined for AML subjects as the number of subjects who achieve the best response of CRc (CR, CRp or CRi) divided by the number of subjects in the analysis population.
  - Response to treatment will be defined per Cheson et al., 2003
  - Response rates will be calculated and their 2-sided 90% confidence intervals will be constructed by Clopper-Pearson method by dose level for phase 1 and by dose level and disease type for phase 2.
- MDS
  - CR + BM CR + PR rate is defined for MDS subjects as the number of subjects who achieve the best response of CR or BM CR plus the number of subjects who achieve the best response of PR divided by the number of subjects in the analysis population.
  - Response to treatment will be defined per Cheson et al., 2006
  - Response rates will be calculated and their 90% confidence interval will be constructed by Clopper-Pearson method by dose level for phase 1 and by dose level and disease type for phase 2.

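### SAP Table 1 and the text definitions give some AML visits a different CRc status, and the SAP does not say which governs the primary endpoint

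*SAP*

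**What the plan says.** The AML primary endpoint is the CRc rate. SAP 6.4.1 defines it by "the number of subjects who achieve the best response of CRc (CR, CRp or CRi) divided by the number of subjects", the denominator being the relevant analysis set. SAP 5.1.1 says that for CRc at a visit "they must achieve CR, CRp or CRI at the visit".

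The text of SAP 5.1.1 and Protocol 7.1.1.1 defines the components:
- **CR** needs ANC >=1, platelets >=100 (all counts x 10^9/L), one week without red-cell or platelet transfusion, and no Auer rods.
- **CRp** is CR except that platelets are <100. Transfusion independence still applies.
- **CRi** is CR except for residual neutropenia, ANC <1, "with or without complete platelet recovery. RBC and platelet transfusion independence is not required".
- **CRh** needs marrow blasts <5%, ANC >=0.5 and platelets >=50. It excludes only subjects who are CR, so the text lets CRh overlap with CRi and CRp.

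The text then closes the list without CRh: "In any case response cannot be categorized as CR, CRp, CRi, PR or NE, it will be categorized as NR".

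SAP 5.1.1 goes on: "A complete response classification schema is presented in" Table 1. That table has one response value per row, in the order CR, CRp, CRh, CRi, PR, PR, NE, NR. Its CRi row has no ANC, platelet or transfusion condition. Its last row, which begins "Any case that cannot be categorized as CR", names CRh among the categories. The best-response order is "the best measured response to treatment for all visits (in the order of CR, CRp, CRI, PR, NR and NE", again without CRh.

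SAP 6.4 makes the derived response primary and refers for its definitions to a Section 7.1.1.

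**The concern.** Table 1 and the text should be two forms of one rule, but they treat CRh differently. In the text, CRh is a description that can coexist with CRi. In Table 1 it is a category of its own, placed ahead of CRi. A visit that lands there is outside CRc and has no rank in the best-response order.

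The CRi row is so open that it would also take every CR and CRp visit. The natural way to get one value per visit is therefore to read the table from the top and stop at the first match. The SAP does not state that rule, or any other.

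Two programmers could follow the SAP in good faith and obtain different CRc counts from the same data. That count drives the futility looks at 12 and 32 subjects and the final criterion of at least 12 responders in 52 (Protocol 9.4.1.3).

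**Working it through.** **1. Classification.** Take marrow blasts <5%, peripheral blasts <=2%, no extramedullary disease and no Auer rods. Apply Table 1 from the top down, then apply the text.

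| ANC | Platelets | Recent transfusion | Table 1 | Text | CRc: table / text |
|---|---|---|---|---|---|
| >=1 | >=100 | no | CR | CR | yes / yes |
| >=1 | 50 to <100 | no | CRp | CRp and CRh | yes / yes |
| >=1 | <50 | no | CRp | CRp | yes / yes |
| 0.5 to <1.0 | >=50 | either | CRh | CRi and CRh | **no / yes** |
| 0.5 to <1.0 | <50 | either | CRi | CRi | yes / yes |
| <0.5 | any | either | CRi | CRi | yes / yes |
| >=1 | >=50 | yes | CRh | CRh | no / no |
| >=1 | <50 | yes | CRi | none of CR, CRp, CRi | **yes / no** |

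Two groups change CRc status, in opposite directions. In the second row, Table 1 also drops a text-CRh visit from the CRh and CR/CRh rates (SAP 5.1.3 and 5.1.4).

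With Auer rods present, ANC >=0.5 and platelets >=50, Table 1 reaches CRh before its own PR row, while the text makes the visit PR and, because its CRh definition is silent on Auer rods, also CRh. Neither is in CRc.

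**2. The plan's own power.** Inputs: p1 = 0.30, p0 = 0.15, power about 0.83, type I error at most 0.10 (Protocol 9.1, SAP 3). Stage sizes are 12, 20 and 20. The AML futility limits are <=1/12 and <=5/32 in the protocol, and <=1/12 and <=6/32 in SAP 6.7.

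With X1 ~ Bin(12, p), X2 ~ Bin(20, p) and X3 ~ Bin(20, p), independent:

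P(success) = P(X1 >= 2, X1+X2 >= c, X1+X2+X3 >= 12), where c = 6 (protocol) or 7 (SAP).

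- Protocol limits: 0.829 at p = 0.30 and 0.067 at p = 0.15. The stated 0.83 is reproduced.
- SAP limits: 0.801 at p = 0.30 and 0.059 at p = 0.15.

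**3. Illustration of a loss.** Let f be the share of true CRc responders whose only qualifying visits fall in the CRh row. The documents do not give f, so it is assumed. The counted rate is 0.30 x (1 - f), with no offsetting gain from the other discordant group.

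| f | Counted rate | Power, protocol limits | Power, SAP limits |
|---|---|---|---|
| 0 | 0.30 | 0.829 | 0.801 |
| 10% | 0.27 | 0.708 | 0.674 |
| 20% | 0.24 | 0.542 | 0.506 |
| 30% | 0.21 | 0.352 | 0.323 |

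A single recoded subject can matter at the first look, where 2 of 12 continues and 1 of 12 stops. At p = 0.30, exactly 2 of 12 has probability 66 x 0.3^2 x 0.7^10 = 0.168.

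**4. Why the CRh row cannot simply be deleted.** With the CRh row gone and the CRi row unchanged, transfused subjects with ANC >=1 and platelets >=50 fall through to CRi and count as CRc, which the text does not allow. If this raised a counted null rate of 0.15 by an assumed tenth or fifth, to 0.15 x 1.10 = 0.165 or 0.15 x 1.20 = 0.18, the chance of declaring success under the protocol limits would rise from 0.067 to 0.116 or 0.181, above the 0.10 cap. With ANC <1 restored in the CRi row, the table and the text agree on CRc in every row of the grid.

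**The case against.** A reader might infer that the primary CRc rate will be understated because these CRi responders are coded CRh and lost. The documents do not support that as a certainty:

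- No passage says that Table 1 is read first-match.
- SAP 6.4 bases the derived response on a Section 7.1.1. The SAP has no such section, and Protocol 7.1.1 contains the text definitions and no Table 1. Under that text the visit is CRi and counts as CRc.
- CRc, the best-response order and the text NR rule all omit CRh. This fits CRh being meant as an overlay for its own rates, and then no responder is lost.
- Even on the top-down reading, only CRi visits with ANC 0.5 to <1.0 and platelets >=50 are affected. A subject leaves the numerator only if no other visit is CR, CRp or CRi.
- The table also adds responders whom the text excludes.

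All of this stands, and it limits the claim. It does not remove the conflict. The intended reading has to be pieced together from a cross-reference to a section the SAP does not have, while the SAP presents Table 1 as the complete schema. Investigator-reported response offers a cross-check, but SAP 6.4 makes it supportive only.

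**Conclusion.** Table 1 and the text give different CRc status in two groups of AML visits, and the SAP does not say which governs. On the natural top-down reading, one group may drop out of the primary numerator and the other may enter it wrongly. The size of each group is not in the documents, so the net direction is unknown.

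The power figures show sensitivity only. They rest on assumed shares of 10% to 30%, a true CRc rate of 30%, no offsetting gains, and the text being the intended definition. What is certain is narrower: the coding rule for the AML primary endpoint is ambiguous in the current SAP, and the ambiguity can be removed at almost no cost. It should be resolved before the response derivation is finalised.

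**What to change.** Make these changes to SAP 5.1.1 and 6.4 in one edit:

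1. Take CRh out of the Table 1 hierarchy. Derive it as a separate yes/no flag at each visit from the text definition, and use the flag for the CRh and CR/CRh rates and their durations.
2. Restore the ANC <1 x 10^9/L condition in the CRi row. This must accompany step 1; otherwise transfused subjects with ANC >=1 are counted as CRc.
3. Word the NR row as in the text: not CR, CRp, CRi, PR or NE.
4. Derive CRc and best response from that column only, and correct the Section 7.1.1 reference in SAP 6.4 so that one set of definitions governs.

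A transfused subject with ANC >=1 and platelets >=50 will then be NR in the response column with the CRh flag set. This follows from the text and is worth a footnote.

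Separately, reconcile the CRh and PR text on whether CRh may be set when Auer rods are present. This does not affect CRc. Adding an Auer-rod condition would change the protocol's definition of a secondary endpoint, so it is more than a table correction.

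The cost of steps 1 to 4 is a SAP table edit and a small programming change, with no new data.
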